## 1. Schedule of Activities

| Visits                            | Screening | Baseline | 1      | 2 | 3 | 4 | 5      | 6 | 7 | 8      | 9 | 10 | Post Tx | Follow-up  (Repeated) |
|-----------------------------------|-----------|----------|--------|---|---|---|--------|---|---|--------|---|----|---------|-----------------------------------|
| Assessments                       |           |          | Week 1 |   |   |   | Week 2 |   |   | Week 3 |   |    |         |                                   |
| Inclusion/Exclusion               | X         | X        |        |   |   |   |        |   |   |        |   |    |         |                                   |
| Consent                           |           | X        |        |   |   |   |        |   |   |        |   |    |         |                                   |
| Psychiatric Interview             |           | X        |        |   |   |   |        |   |   |        |   |    |         |                                   |
| HRSD, MoCA, WSAS, GAD7            |           | X        |        |   |   |   |        | X |   |        |   |    | X       |                                   |
| MRI / MRS                         |           | X        |        |   |   |   |        | X |   |        |   |    | X       |                                   |
| QIDS                              |           |          | X      | X | X | X | X      | X | X | X      | X | X  |         |                                   |
| Randomization         |           | X        |        |   |   |   |        |   |   |        |   |    |         |                                   |
| Standard Monitoring               |           |          | X      | X | X | X | X      | X | X | X      | X | X  |         |                                   |
| EEG                               |           |          | X      | X | X | X | X      | X | X | X      | X | X  |         |                                   |
| Blood Sample                      |           |          | X      |   |   |   |        |   |   |        |   | X  |         |                                   |
| Anesthetic Induction  |           |          | X      | X | X | X | X      | X | X | X      | X | X  |         |                                   |
| Anesthetic Emergence  |           |          | X      | X | X | X | X      | X | X | X      | X | X  |         |                                   |
| QIDS, WSAS, Study XP  |           |          |        |   |   |   |        |   |   |        |   |    |         | X                                 |

 Study 1 only

 High ISO/BS+, Low ISO/BS-, or propofol

 Time to eye opening, time to sitting without dizziness, and time to ambulation and ingestion of liquids without vomiting. Occurrence rates of nausea and vomiting, presence of EKG abnormalities and somatic complaints, and total time for each will also be recorded. Orientation time will be assessed as the earliest time post-treatment at which a participant is able to recall 4 of 5 orientation items (name, date of birth, age, place, day of the week).

 An opened ended question about the participant's experience during the study

 Follow-up measures will take place monthly after the end of treatment series and will continue for 6 months.

## 2. Study Objectives

### 2.1 Study 1

Study 1 will test the central hypothesis that high dose isoflurane anesthesia inducing EEG burst suppression (High ISO/BS+) is a more effective intervention for severe depression when compared to a low dose isoflurane anesthesia that does not induce EEG burst suppression (Low ISO/BS-). The proposed study is a randomized, double-blind trial that will evaluate 30 actively depressed participants with moderate to severe depression. Depression outcomes will be compared between two groups of participants (n=15 per group) who have received 10 treatment applications over a period of three weeks of either High ISO/BS+ or Low ISO/BS-.

Aim 1. To determine whether High ISO/BS+ is more effective than Low ISO/BS- in producing either a treatment response (defined as 50% reduction in depression scores) or full remission of depressive symptoms. We hypothesize that significantly more depressed participants randomized to receive 10 treatments of High ISO/BS+ compared to Low ISO/BS- will show a positive treatment response or full remission by treatment end. Based on the STAR\*D Trial, a responder is a participant showing 50% reduction in depression score and full remission is defined as a score of 0-10 on the HRSD-24 scale and score of 0-5 on the QIDS-SR16.

Aim 2. Preliminary data on neural and immune pathways that are differentially affected by the 2 treatments and associated with antidepressant effects will be explored by comparing changes from pre-treatment to post-treatment in full transcriptome leukocyte gene expression (using the RNA Seq method).

Aim 3. To measure the central neurochemical effects of isoflurane treatment, we will quantify neurotransmitter levels (GABA and glutamate) using magnetic resonance spectroscopy.

### 2.2 Pilot Study 2

Study 2 is designed to complement Study 1 in providing additional support for the hypothesis that burst suppression is an important mechanism for antidepressant treatment effects of anesthesia in moderate to severe depression. If Study 1 demonstrates that more participants receiving High ISO/BS+ undergo remission than those receiving Low ISO/BS-, this could be interpreted as a dose response effect for isoflurane that is not specifically a result of burst suppression. Demonstrating that a different anesthetic administered at doses producing 80% burst suppression for 10 treatment session is also effective in producing depression remission would add support for the hypothesis that the underlying mechanism is burst suppression. Therefore, Study 2 will be an open-label trial to provide preliminary data that propofol, an intravenous anesthetic with a favorable safety profile, administered for 10 treatment sessions at levels to induce 80% burst suppression, also is effective in producing depression remission in 50% or more of the pilot sample of 10 depressed participants.

Aim 4. To determine whether propofol anesthesia at a level to produce 80% EEG burst suppression is effective in producing remission of depressive symptoms. We hypothesize that

the majority of depressed participants (n=10) receiving 10 treatments of propofol anesthesia will achieve remission of symptoms by treatment end.

Aim 5. Preliminary data on neural and immune pathways that are differentially affected by the 2 treatments and associated with antidepressant effects will be explored using full transcriptome leukocyte gene expression (RNA Seq).

Aim 6. To measure the central neurochemical effects of propofol treatment, we will quantify neurotransmitter levels (GABA and glutamate) using magnetic resonance spectroscopy.

### **3. Background**

Major Depressive Disorder is a prevalent, chronic, recurring disorder that is becoming increasingly burdensome both to individuals and society at large. Despite the increasing burden of this disease, we have seen a plateau in development and establishment of effective treatments, particularly for those who are refractory to conventional medications. Electroconvulsive therapy (ECT) is typically regarded as the treatment of choice for the most treatment resistant depression (TRD) as it rapidly reduces symptoms and yields high remission rates (about 55-90%) even after multiple medication failures. Though effective, ECT is associated with significant adverse cognitive effects such as retrograde amnesia, problems with concentration and attention, and other cognitive sequelae. There is also a widespread public misunderstanding that the seizure induced by ECT may be painful, and carries risk of brain damage and personality change. These fears make patients and family members reluctant to approve this treatment option. For these reasons, this effective therapy is often used a treatment of last resort (relegated to 5th, 6th or 7th step after the failure of other therapies per American Psychiatric Association guidelines) and ECT is administered to only about 100,000 of the millions of TRD patients each year. For TRD patients, there is a great need for alternative therapies with similar efficacy to ECT but wider social acceptability and less adverse cognitive effects.

One such treatment alternative that may be both efficacious and have a better side effect profile is deep inhalation anesthesia with isoflurane. Like ECT, deep anesthesia with isoflurane induces a brief state of electrocortical quiescence (flat electroencephalogram), but does not induce convulsions or other seizure symptoms. Anesthesia-induced cortical burst suppression was first suggested as a potential alternative to ECT for treatment resistant depression in the 1980's. Recent research, both clinical and preclinical, has renewed interest in this hypothesis.

Langer et al originally hypothesized that high dose isoflurane anesthesia (High ISO) might be an effective antidepressant therapy based on certain similarities to the physiological effects of ECT. The feature shared by High ISO and ECT was a reduction in electrocortical activity, which occurs after the seizure in ECT and without any seizure in High ISO anesthesia. In their study of ECT treatments, Kranaster et al noted that post-ictal burst suppression index correlated with seizure duration, and thus was predictive of antidepressant effectiveness. The hypothesis that cortical burst suppression (BS+) is important in anesthesia-induced antidepressant effects has

not been rigorously studied in patients, but has been reinforced by recent findings using animal models of depression including research by our co-investigators. Murrell et al had previously reported that at equivalent anesthetic concentrations, isoflurane had greater potency to induce BS+ than 2 related anesthetic drugs, sevoflurane and desflurane, and that another inhaled anesthetic, halothane, did not induce burst suppression (BS-). Using the forced swim test, [name] et al found that High ISO anesthesia had antidepressant effects in mice similar to the antidepressant desipramine. Similarly, using a shuttle box-based test of learned helplessness in rats, Wang et al found that 2 hours of isoflurane at 2% prevented this depressive behavior while halothane-treated rats (who experienced no EEG burst suppression) showed no preventive antidepressant effects. Whether cortical burst suppression is the mechanism for the antidepressant effect of isoflurane anesthesia in patients and animal models remains an important and unresolved research question.

Initial trials examining the antidepressant efficacy of High ISO were promising. Langer et al conducted two preliminary studies that demonstrated comparable efficacy between 6 sessions of High ISO vs. ECT, with High ISO having the advantage of not causing memory loss. Antidepressant efficacy was also supported by Engelhardt et al who used High ISO treatments followed by ECT and by Carl et al who again found comparable antidepressant efficacy with the 2 treatments. These positive findings were followed by two negative trials. Greenberg et al treated 6 elderly individuals with High ISO, with little improvement. Garcia-Toro et al examined the efficacy of 4 low dose treatments of a related anesthetic, sevoflurane, in another pilot trial, and saw a 24% reduction in depressive symptoms. Since sevoflurane is less effective in inducing BS+ than isoflurane, the dose could have been too low to achieve consistent BS+. Moreover, 4 treatments are fewer than are recommended for ECT (8-12 sessions) and thus it is not surprising that the effect size was small. Unfortunately, further investigations of High ISO as an antidepressant halted for quite some time.

Because of its early success and the design limitations associated with the negative trials, our group conducted a small open-label study to renew investigation of the potential antidepressant efficacy of High ISO. In the study, 8 patients with treatment resistant depression were treated with 10 sessions of high dose ISO with confirmed EEG burst suppression (High ISO/BS+). The comparison group was 20 patients treated with bifrontal ECT. High ISO/BS+ led to an antidepressant response (defined as a 50% reduction in HRSD score) in 75% of participants and a rate of full remission of depressive symptoms identical to ECT (50%). Furthermore, the response rates for the High ISO/BS+ and ECT treatments were comparable, as measured by QIDS self-report. In addition, improvement was maintained for 4 weeks after treatment for most participants in the High ISO/BS+ group. Furthermore, participants treated with High ISO/BS+ showed significantly less neurocognitive impairment following their treatments than was shown by ECT-treated patients.

The central question in the proposed research is whether isoflurane-induced cortical burst suppression (BS+) is necessary for antidepressant efficacy in patients with severe depression. We demonstrated that BS+ (defined as  $\geq 80\%$  burst suppression ratio (BSR) using the Bispectral Index BIS Monitor) can be reliably induced at high isoflurane concentrations that are clinically

safe in our target population while on various psychotropic medications. However, to date, there has been no rigorous randomized, blinded trial comparing antidepressant effects of High ISO/BS+ to an appropriate control condition. The present study is designed to provide this rigorous test using a control condition involving a lower isoflurane dose that predictably produces unconsciousness in this same patient population without causing burst suppression (BS-, defined as  $\leq 20\%$  BSR). Thus, we will determine if high dose ISO anesthesia inducing EEG burst suppression (High ISO/BS+) is a more effective intervention for severe depression when compared to a low dose ISO that does not induce EEG burst suppression (Low ISO/BS-).

As an additional test of whether cortical burst suppression is a possible mechanism underlying anti-depressive effects of deep anesthesia, we will also examine the antidepressant effects of burst suppression induced by propofol, an intravenous anesthetic with a favorable safety profile that is routinely used by anesthesiologists. This closely associated study will be an open-label trial to provide preliminary data that may support the use of propofol for this group of depressed patients. Propofol is the agent of choice to induce burst-suppression for brain protection during neurosurgical procedures and is used routinely for this purpose. Propofol does not promote post treatment nausea; however, like isoflurane, propofol is associated with dose dependent hypotension. This is well tolerated by patients without cardiovascular disease and is easily treated as described for isoflurane. Although anecdotal data support some anti-depressant effects with propofol, these effects have not been specifically or systematically examined. If effective, its use may be an even better option than isoflurane for patients, for the reasons described above.

If evidence from these studies support deep anesthesia with BS+ (High ISO/BS+ and/or propofol/BS+), it would point to a possible mechanism of action for the antidepressant effects of deep anesthesia. Treatments that evoke burst suppression, in theory, could have all the benefits of ECT without the neurocognitive deficits and the associated social stigma.

As detailed above, even in the minority of cases when initial pharmacological treatment for depression is effective, it usually requires months before symptoms show satisfactory remission, and during that time patients and physicians have no objective test to use to verify that the intervention is or is not likely to be successful. Even with ECT, where improvement can be noted in days rather than weeks or months, initial signs of improvement are based on relatively soft non-objective measures such as global improvement that rely heavily on the physician's individual clinical insight and experience. Thus, there is a great need to establish convenient, reliable and objective biomarkers for treatment-induced changes that reliably predict clinical improvement in cases of depression.

By comparing changes in full transcriptome leukocyte gene expression from pre- to post-treatment in these 40 participants treated with High ISO/BS+ vs. Low ISO/BS-, and propofol/BS+, this investigation will explore the neural and immune pathways through which anesthetic-induced antidepressant effects are produced, and will be able to identify candidate neural pathways that can later be reconfirmed in larger samples. In particular, we will examine the possible role of NMDA receptor subunits, GABA-ergic and ATP-responsive ion channel

pathways as well as other putative depression- or suicidality-linked neuroimmune pathways previously associated with refractory depression or suicidality by our group and others.

Burst suppression anesthesia is thought to strongly engage the brain's major inhibitory and excitatory neurotransmitter systems, GABA and glutamate, respectively. Indeed, both isoflurane and propofol are thought to directly bind GABA and glutamate receptors. To better understand the brain mechanisms through which burst suppression causes antidepressant effects, we will measure GABA and glutamate concentrations in vivo using magnetic resonance spectroscopy, a type of MRI.

## **4. General Study Design**

To determine if the antidepressant effects of deep anesthesia are related to burst suppression (BS+) we will conduct two concurrent studies: 1) prospective, randomized, double-blind study will evaluate the role of burst suppression using isoflurane treatments at 2 doses (high dose ISO/BS+ vs low dose ISO/BS-) on symptoms in participants with moderate to severe depression, and 2) an open-label pilot study examining the anti-depressive effects of propofol anesthesia, BS+ same as high dose ISO/BS+ on symptoms in participants with moderate to severe depression.

### **4.1 Inclusion Criteria**

We will recruit depressed patients referred to the University Neuropsychiatric Institute for an ECT consult.

- Diagnosis of Major Depressive Disorder (MDD) or bipolar Disorder (I or II, most recent episode must be depression)
- Failed at least 2 anti-depressant treatments and no ECT in past 6 months
- Age between 18-55 years
- BMI < 40
- Hamilton Rating Scale for Depression (HSRD) score > 18
- Quick Inventory of Depression Scale (QIDS) score > 10.

### **4.2 Exclusion Criteria**

- Diagnosis of other current and/or active DSM-5 disorders with the exception of anxiety disorders
- Significant pre-morbid cognitive impairment
- Hypertension and current use of ACE inhibitor or AR blocker medications
- Symptomatic coronary artery disease or congestive heart failure
- History of transient ischemic or neurologic signs during the past year
- History of or susceptibility to malignant hyperthermia
- Contraindication to isoflurane or propofol anesthesia (as determined by anesthesiologist)
- Diabetes requiring insulin
- Poor kidney function
- Chronic use of benzodiazepines or opioids

- Individuals incompetent to provide consent (e.g. catatonic, psychotic).

### **4.3 Study Recruitment Procedures**

Potential participants will be recruited to the study through one of three ways: chart review, referral, or direct enrollment.

Recruitment via chart review: Potential participants will first be identified through review of medical records by trained study staff; specifically, examination of the records of patients who have been scheduled for an ECT consultation at the University Neuropsychological Institute (UNI). Participants who may be eligible for screening will be told about the study toward the end of their consultation. Interested patients will be screened and consented either right after the ECT consultation or during a separate appointment.

Recruitment via referral: Physicians from the Department of Psychiatry who have been informed of this study may also refer patients for screening. Patients who are referred will be contacted by study staff to arrange for screening and consent.

Direct enrollment: Psychiatrists listed on the study protocol may identify potential research volunteers during their ECT consultations. These patients will be informed of the research, and if interested, will be screened and consented.

Participants will be informed that there are two study options and that they will be able to decide which one they will participate in. For the isoflurane study, we will explain that some preliminary evidence shows that high dose isoflurane is effective in reducing depression symptoms. However, if the isoflurane study is chosen, there is a 50:50 chance of being in the low dose isoflurane treatment, and the individual will not know what treatment group (high vs low dose) they are in. We do not know whether low dose isoflurane will reduce depression symptoms. For the propofol study, we will explain that this arm of the study is open-label, meaning they will know they are receiving propofol treatment at a dose that produces burst suppression. We will also inform participants that we do not know if propofol treatment will be effective in reducing symptoms of depression.

We hope to enroll at least 1 participant per week and have a maximum capacity of 4 participants per week with a total of 45 participants enrolled in the study (30 in Study 1 and 10 in Study 2).

### **4.4 Informed Consent Procedures**

Trained research staff will screen potential participants and obtain consent. Participants will be consented in the physician's office (if consent is after the ECT consult); otherwise, consent will take place in a private meeting room near the ECT Clinic at UNI. No other language than English will be used to obtain consent.

Participants and study coordinator (and/or physician) will go over each section of the consent form together. They will then be given time to read/ think about/ discuss/ and ask questions

about the study before they sign. Thus, they may sign at that time, or we may schedule another visit to sign and enroll into the study. Most of these patients have a support person with them who will be included in the consent process (provided the participant is fine with it). A legally authorized representative (LAR) will NOT be used to consent the participant.

We will make certain the participant understands that the experimental treatments may or may not be effective. We are not offering any financial inducement for participation. Participants are not required to sign the consent right after we explain it. If necessary, we will schedule a later date for consent to allow adequate time for participants to ask questions and think about whether to participate in the study.

Psychiatrist Investigators on this protocol may consent patients if they see an eligible patient in a context other than an ECT consult. We don't anticipate that many participants will be enrolled via this route.

#### **4.5 Study Visits**

**Screening:** Patients who have been referred or have volunteered for the study will be screened in person or by phone to verify that inclusion and exclusion criteria have been met.

**Consent procedures:** Each patient will be given a full verbal explanation of the study procedures, including risks, benefits, and alternatives, and will be given a copy of the approved written consent form. The patients will be given the opportunity to review the consent form and to discuss any questions or concerns with their own psychiatrist, our study investigators, or others if necessary prior to beginning study treatment procedures.

**Baseline:** Prior to the first treatment, depression severity will be assessed via a psychiatric interview, including completion of the HRSD-24 and MoCA, which will also verify inclusion and exclusion criteria. Immediately before treatment 1, the participant will complete the QIDS and a blood sample will be obtained from the IV line.

**Randomization (Study 1 only):** Participants who meet study criteria will be randomly assigned in blocks of 4 to either high or low dose isoflurane (High ISO/BS+ vs. Low ISO/BS-). We anticipate up to 15 participants in each arm; this sample size was defined by our prior study in which 8 participants were adequate to show significant antidepressant effects.

**Leukocyte Gene Expression:** Although our study is designed with EEG burst suppression as our primary target mechanism, we acknowledge that its effects must be mediated via specific neural pathways. Thus, we will explore possible neural and immune pathways associated with the antidepressant effects of deep anesthesia. Changes in full transcriptome leukocyte gene expression from pre- to post-treatment will be assessed from blood samples drawn before the first treatment and within 48 hours of the final (10th) treatment. In particular, we will examine the possible role of GABA-ergic and ATP-responsive ion channel pathways as well as other putative depression- or suicidality-linked neuroimmune pathways. We will also evaluate other ATP-responsive ion channels (purinergic, acid sensing and transient vanilloid receptor) or other

genes including IL-10 and other cytokines, SAT1, PTEN, MARCKS and MAP3K3 previously associated with refractory depression or suicidality by our group and others. [42918](#)

**Magnetic resonance imaging:** GABA and glutamate concentrations will be quantified in the prefrontal cortex and a posterior cortical control region using 2-dimensional J-resolved proton magnetic resonance spectroscopy (MRS) and prior knowledge fitting (Prescot & Renshaw, 2013) on the Siemens Prisma 3T scanner at the Imaging & Neurosciences Center in Research Park. In case that scanner is unavailable, images will be acquired using an identical scanner at the University Neuropsychiatric Institute. Time in the scanner is expected to be 60-75 minutes (maximum: 90 minutes). The scans will be completed prior to beginning the treatments, before treatment #6, and 48-72 hours post treatment #10.

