## **5. Clinical and Laboratory Evaluations**

### **5.1 Study Drug Administration and Duration**

All treatment groups, High ISO/BS+, Low ISO/BS- (Study 1) and propofol (Study 2) will receive 10 treatments over 3 weeks. All treatment procedures will take place in the ECT Procedure Room at the University of Utah Neuropsychiatric Institute. All participants will receive standard monitoring as recommended by the American Society of Anesthesiologists that includes EKG, pulse oximetry, blood pressure by noninvasive cuff, temperature, respiratory rate, and end-tidal carbon dioxide. If monitoring reveals significant hemodynamic alteration the anesthesiologist will manage the study participant by one or more of the following: IV fluid loading; Trendelenburg positioning; small bolus doses of ephedrine, phenylephrine, or epinephrine; or stopping the anesthesia. The course of action will be at the discretion of the anesthesiologist based on initial hemodynamics, absolute MAP change, and condition of the study participant. IV fluids will also be co-loaded at induction with the goal of replacing any deficit that resulted from fasting. The above noted anesthetic practices are routine and carried out on a daily basis in both the operating room and in the ECT suite.

**5.1.1 Study 1. High vs Low Dose Isoflurane (ISO):** The route and doses of isoflurane (both high and low doses) fall within the normal range of standard clinical practice. Details of induction follow, below:

Anesthetic Induction (High and Low Dose ISO): Anesthetic induction will be achieved with methohexital (1-3mg/kg IV). If there is a contraindication to methohexital, etomidate or propofol will be administered at the discretion of the anesthesiologist. General anesthesia will be administered via facemask. Patients will be co-loaded with IVF to offset any dehydration from fasting. Patients will be ventilated while under anesthesia using an LMA or ET tube as appropriate for safety and comfort.

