## **5.2 Study Drug Management**

Study drug will be managed by staff at the University Neuropsychiatric Institute. Subjects will be issued a subject ID number. This number will be used to randomize subjects into High ISO/BS+ or Low ISO/BS- arms of the study. Randomization will be conducted by a designated un-blinded member of the study team. Emergency un-blinding information will be maintained by a designated custodian. Subjects' un-blinding information will only be accessed by the study team in case of a medical emergency. If a drug disclosure is made, a record must be made by the Investigator detailing the purpose, date, and personnel involved.

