## **5.3 Clinical Assessments**

**5.3.1 Primary Response Assessments:** The primary outcome measure is change in depressive symptoms assessed by the Hamilton Rating Scale for Depression (HRSD-24), which is the most widely used method of evaluating the effectiveness of treatments to relieve depression. HRSD-24 will be administered as part of a clinical interview by blinded investigators prior to beginning the treatments, then repeated before treatment #6 and at the end of treatments.

**5.3.2 Secondary Response Assessments to be acquired before each treatment:** Also as standard of care for patients receiving ECT, the participant will fill out the Quick Inventory of Depressive Symptomatology (QIDS-SR) which is a patient self-report measure of depressive symptoms prior to each treatment session. QIDS scores will also be used as a safety measure. If 2 consecutive QIDS scores indicate worsening of depressive symptoms, below pre-treatment values, the study participant will meet with one of the study Psychiatrists to discuss treatment alternatives. The Montreal Cognitive Assessment (MoCA), Generalized Anxiety Disorder scale (GAD-7), and Work and Social Adjustment Scale (WSAS) will be administered prior to beginning the treatments, then repeated before treatment #6, and 48-72 hours post treatment #10.

**5.3.3 Follow-up Assessments to be acquired monthly for up to 6-months post treatment period:** Follow-up assessments will include QIDS-SR, WSAS, and an opened ended question about the participant's experience during the study. Follow-up assessments will be administered over the phone or by email with a link to an electronic survey housed on REDCap (a secure online database). A voicemail may be left (with prior permission) regarding the follow-up assessments.

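### With one stated block size of 4, an expected 9 of 30 Study 1 assignments are certain in advance to anyone who knows the earlier ones, and the available text does not keep such people away from enrollment

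*Combined protocol and SAP*

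**What the plan says.** Section 4.5 describes the randomization in one sentence: "Participants who meet study criteria will be randomly assigned in blocks of 4 to either high or low dose isoflurane". No other block size and no strata are mentioned. Allocation is equal: Section 4.3 tells candidates that "there is a 50:50 chance of being in the low dose isoflurane treatment". On size, Section 4.5 says "We anticipate up to 15 participants in each arm". There is one treatment location (Section 5.1): "All treatment procedures will take place in the ECT Procedure Room at the University of Utah Neuropsychiatric Institute".

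On who knows the assignments, Section 5.2 says: "Randomization will be conducted by a designated un-blinded member of the study team". The same section gives the emergency codes to a custodian and allows the study team to consult them only in a medical emergency. Sections 2.1 and 4 call Study 1 double-blind, and Section 5.3.1 says "HRSD-24 will be administered as part of a clinical interview by blinded investigators".

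On entry to the trial, Section 4.3 says: "Participants will be informed that there are two study options and that they will be able to decide which one they will participate in". Research staff screen and obtain consent (Section 4.4). Psychiatrists on the protocol may identify candidates (Section 4.3) and in some circumstances consent them (Section 4.4). Section 4.2 leaves contraindication to the study anesthetics to an anesthesiologist's judgment.

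**The concern.** Permuted blocks protect against selection only while past assignments stay hidden. Once they are known, a fixed and published block size turns some future assignments into certainties. Two features of this trial make that knowledge possible outside the randomization office.

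- **Titration.** Section 5.1.1 has isoflurane adjusted against a continuously displayed burst-suppression ratio, with a goal of 80% in one arm and 20% or less in the other. Whoever titrates can tell the arm. Section 4.2 gives the anesthesiologist role a say in eligibility, and nothing says that the two tasks fall to different people.
- **Deterioration.** Section 5.3.2 sends a participant with two consecutive worse QIDS scores to a study psychiatrist to discuss alternatives. Under Section 6.3 the offer depends on the arm: High ISO or ECT after Low ISO, and ECT only after High ISO. That conversation can disclose the assignment to someone who may also recruit or consent.

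Candidates choose between two studies after counseling, and consent may be scheduled for a later date (Section 4.4). Someone who expected a particular next assignment could therefore influence who enters Study 1, or when, without breaking any stated rule. With 15 per arm, one participant moves an arm's response rate by 1/15 = 6.7 percentage points. Section 7.1 commits to baseline severity as a covariate and leaves others to need, so adjustment would offer limited repair.

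**Working it through.** The plan gives no figure for predictability, so there is none to reproduce.

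**Inputs.** Block size 4 (Section 4.5); 1:1 allocation (Section 4.3); 30 randomized, 15 per arm (Section 2.1). Assumption: the observer knows the block start and all earlier assignments in the block.

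**Certain assignments.** A 1:1 block of 4 has 6 equally likely orders.
- Positions 1 and 2 are never determined.
- Position 3 is determined when the first two are alike: 2 of 6 orders, or 1/3.
- Position 4 is always determined.

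The expected number per block is 0 + 0 + 1/3 + 1 = 4/3, which is 33.3% of a complete block. Thirty participants make 7 complete blocks plus 2, because 7 × 4 = 28, and those last 2 are never determined. The expectation is 7 × 4/3 = 9.33, and 9.33/30 = 31.1%. Each complete block contributes 1 or 2 certain assignments, so the range is 7 to 14 (23% to 47%).

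**Best guess.** The observer always names the arm with more places left. The chance of being right at positions 1 to 4 is:
- position 1: 1/2
- position 2: 2/3
- position 3: 1/3 × 1 + 2/3 × 1/2 = 2/3
- position 4: 1

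The sum is 17/6 per block (70.8%). Over 30 it is 7 × 17/6 + 1/2 + 2/3 = 21.0, or 70.0%, against 50% with no knowledge.

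**Final balance.** The two participants in the unfinished block fall in the same arm with probability 2/6 = 1/3. Fixed blocks of 4 therefore already carry a 1 in 3 chance of 16:14.

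**Randomly varied sizes.** This was simulated with 4,000 trials of 30. The observer knows the set of sizes and all earlier assignments, but not the size of the current block.

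| Block sizes | Certain | Best guess correct |
|---|---|---|
| 4 only (exact) | 31.1% | 70.0% |
| 4, 6 | 5.7% | 68.8% |
| 2, 4, 6 | 3.9% | 69.7% |
| 4, 6, 8 | 2.2% | 67.5% |

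Varying the size removes most of the certainty and almost none of the guessing advantage. Only ignorance of past assignments brings the guess back to 50%.

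**The case against.** The strongest reply is that every figure above is conditional on knowledge that the plan does not give to recruiters. That is correct. A reader might infer that a third of assignments will be deducible by recruiting staff in this trial. The documents do not support this: Section 5.2 restricts the study team's access to un-blinding information, Study 1 is labeled double-blind, and for a fully blinded recruiter the share is zero.

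A reader might also infer that staff place people in one study or the other. Section 4.3 gives that choice to the participant, so staff can act only through information, screening and timing.

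The routes of disclosure are also limited. Section 5.2 names one un-blinded person and a custodian, and that anesthesia staff know the arm is an inference from the titration. They are given no recruiting or consenting task; their stated role in entry is to judge contraindication. Offers after deterioration reveal single assignments, not whole blocks. At the capacity of 4 a week, a block could fill before any offer is made. At the hoped-for minimum of 1 a week, a block spans about four weeks or more, so an offer could come while it is still open.

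Some safeguards are partly in place. Only people who meet the criteria are randomized, and the schedule of activities puts consent, HRSD and randomization at the same baseline visit. Section 8 (Training and Resources), listed in the contents, was not in the text available, and it may describe staff roles.

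What remains is that the order of steps at baseline and the separation of roles are not stated, and that a single block size is published where it need not be.

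**Conclusion.** The point holds as a conditional weakness in allocation concealment. If someone with influence on entry knows the block start and all earlier assignments, an expected 9.3 of 30 assignments (31%, range 7 to 14) are certain to that person, and guessing succeeds 70% of the time. Knowing only some earlier assignments gives less, and knowing none gives nothing. These figures assume 1:1 blocks of 4 and exactly 30 randomized. The judgment that concealment is not described rests on the available text.

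Nothing in the documents shows that assignments will leak or that selection will occur, and no bias in the treatment comparison can be calculated from them. The 1 in 3 chance of 16:14 has little consequence in itself. This is a low-severity point, worth acting on because prevention costs almost nothing and selective entry is hard to repair afterward at this sample size.

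**What to change.** 1. Generate the list with randomly varying block sizes, for example 4 and 6, or 4, 6 and 8. Keep the sizes in a restricted document and out of the protocol held by site staff.
2. Have the un-blinded person already designated in Section 5.2 hold the list and take no part in recruitment, eligibility decisions or rating.
3. Release each assignment only after Study 1 consent, all eligibility decisions (including the anesthetic contraindication judgment) and the baseline HRSD-24 are recorded as final.
4. State that past assignments are withheld from everyone who recruits, consents or judges eligibility. Where staffing allows, those who titrate, and those who hold an arm-revealing discussion after deterioration, should not do these tasks for later Study 1 candidates. This is the essential part, because steps 1 and 3 do not hide past assignments from people who saw them in practice.

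The cost is a new list and a few sentences. The downside is that arm sizes may differ by a few participants. All block sizes are even, so at 30 an unfinished block stops after an even number. The largest split is then 16:14 with sizes 4 and 6 (2:0 after two, 3:1 after four), and 17:13 if a block of 8 stops at 4:0. Fixed blocks of 4 can already give 16:14.
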